#### 7.6 Unblinding Procedures

Unblinding will occur when the safety of a patient requires this and will be up to the judgment of the treating physician. The investigators will be notified of such unblinding.

#### Stopping Rules

The study will be stopped when the adverse event rate exceeds that of the expected rate listed above or greater than two serious adverse events occur and are judged to be the direct result of the investigatory agent.

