##### 4.2 Toxicities and Dosing Delays/Dose Modifications

Any patient who receives treatment on this protocol will be evaluated for toxicity per the Toxicity Assessment Survey (attached). Each patient will be assessed for the development of toxicity per the Time and Events Table, and overall study cohort safety will be statistically compared at defined intervals (See Section 5.4).

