### 5. PROCEDURES

#### 5.1 Screening/Baseline Procedures

Assessments performed for clinical indications (not exclusively to determine study eligibility) may be used for baseline values even if the assessments were done before informed consent was obtained. All screening procedures must be performed within 30 days prior to registration unless otherwise stated. The screening procedures include:

- 5.1.1 *Informed consent*
- 5.1.2 *Medical history*  
Complete medical and surgical history, history of urinary retention, benign prostatic hypertrophy, urogenital procedures
- 5.1.3 *Demographics*  
Age, gender, race, ethnicity
- 5.1.4 *Review of subject eligibility criteria*
- 5.1.5 *Review of previous and concomitant medications*
- 5.1.6 *Physical exam including vital signs, height and weight (Standard of Care)*  
Vital signs (temperature, pulse, respirations, blood pressure), height, weight
- 5.1.7 *Adverse event and efficacy assessment*  
Baseline adverse events will be assessed. Efficacy will be assessed periodically as well. Adverse events and efficacy will be considered in continuation of the study at enrollment intervals (See Section 5.4). See Section 7 for adverse event monitoring and reporting.
- 5.1.8 *Hematology-(Standard of Care)*  
CBC with differential
- 5.1.9 *Serum chemistries (Standard of Care)*  
Basic metabolic panel (BMP) to include: BUN, creatinine, electrolytes (sodium, potassium, calcium, chloride, bicarbonate), and glucose

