## 6.0 Response Criteria

### 6.1 Safety/Tolerability

Analyses will be performed for all patients having received at least one dose of study drug.

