### 7.3 Definitions

#### 7.3.1 Definition of Adverse Event

An adverse event (AE) is any untoward medical occurrence in a patient receiving study treatment which does not necessarily have a causal relationship with this treatment. An AE can therefore be any unfavorable and unintended sign (including an abnormal laboratory finding), symptom, or disease temporally associated with the use of an experimental intervention, whether or not related to the intervention.

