**10. STATISTICAL CONSIDERATIONS****10.1 Study Design/Study Endpoints**

Prospective, double blinded, randomized single-center study comparing the efficacy of tamsulosin in reducing POUR incidence in primary total hip and knee arthroplasty patients.

Adverse events will be monitored at intervals of 50 (25 in each group). If AEs in the trial group exceed those in the placebo group, and this difference is statistically significant and related to the active drug (tamsulosin), then the study will be terminated. Minor adverse events will be examined via statistical tests (chi-square) at each interval. If there are severe adverse events noted in the intervention group, the study may be halted until further review.

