### **11.4 Data Management and Monitoring/Auditing**

Study coordinator will continually update an anonymized database of patients, their endpoints, secondary measures, adverse events.

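### The adverse-event limb of the stopping rule does not name its rate, column or arm, makes no allowance for chance, and is not linked to the placebo comparison in Section 10.1

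*Combined protocol and SAP*

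**What the plan says.** The Stopping Rules paragraph has two limbs. The first is mandatory: "The study will be stopped when the adverse event rate exceeds that of the expected rate listed above". The second stops the study after more than two serious adverse events judged to be directly caused by the study agent.

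The only adverse-event rates that precede this paragraph are in Section 7.1.4. That table has an Any row and rows for single events, each with an All column and a Drug related column. The Any row reads 390 (76) and 132 (26). The table appears to come from reference 10, whose title concerns long-term tamsulosin for benign prostatic hyperplasia. It shows no control column.

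Section 10.1 sets out monitoring separately. On timing: "Adverse events will be monitored at intervals of 50 (25 in each group". On the trigger: "If AEs in the trial group exceed those in the placebo group, and this difference is statistically significant and related to the active drug", the study is terminated. It adds that minor events are tested by chi-square at each interval, and that severe events in the intervention group may lead to a halt for review.

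Two other sections point elsewhere for the timing. Section 4.2 says "overall study cohort safety will be statistically compared at defined intervals (See Section 5.4", and Section 5.1.7 says "Adverse events and efficacy will be considered in continuation of the study at enrollment intervals (See Section 5.4". Section 5.4 is a visit table with three columns (pre-operative, inpatient, two-week follow-up) and gives no enrolment intervals.

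Section 6.1 defines the safety population: "Analyses will be performed for all patients having received at least one dose of study drug". Section 7.3.1 defines an adverse event as "any untoward medical occurrence in a patient receiving study treatment which does not necessarily have a causal relationship" with that treatment.

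**The concern.** A rule that obliges the study to stop should be decidable from its own text before any data are seen. This limb is not. The singular wording fits the Any row best, but that row holds two limits, 76% and 26%. The definition in Section 7.3.1 ignores causality and favours the first. Carrying the attribution wording over from the serious-event limb favours the second, although grammatically that wording belongs to the serious-event limb alone. Neither reading settles which arm is counted.

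The limb also treats any numerical excess as an excess. An observed rate from 25 men varies widely around the true rate, so a true rate at or just under the limit will often be exceeded by chance, and several looks add to this.

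The limit is a historical rate from a different setting, yet the trial has a concurrent placebo arm. Events common after joint replacement can push the observed rate over the limit equally in both arms. Section 10.1 would then see no excess while this limb requires a stop. Neither passage refers to the other.

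At stake are an unnecessary termination or, if the looser limit is applied to attributed events, a failure to act. In either case the rule's meaning might be chosen after the data are known.

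**Working it through.** **Inputs.** Limits 76% and 26% (Section 7.1.4, Any row). Looks every 50 patients, 25 per arm (Section 10.1). Enrolment of 114 per arm, 228 in total (Section 10.2). The plan states no false-stop probability, so there is no figure of its own to reproduce on this point. The enrolment figure does reproduce: 91 / 0.80 = 113.75, rounded up to 114, and 2 × 114 = 228. Since 228 / 50 = 4.56, there are four full looks, at 25, 50, 75 and 100 tamsulosin patients.

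**Assumptions.** One yes/no indicator per patient, the tamsulosin arm counted, all-cause counts set against 76%, and attributed counts set against 26%.

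**Boundary as written.** The rule fires at look n if the count X exceeds n × limit, so the smallest firing count is floor(n × limit) + 1.
- 76%: 25 × 0.76 = 19, 50 × 0.76 = 38, 75 × 0.76 = 57, 100 × 0.76 = 76. Firing counts are 20, 39, 58 and 77.
- 26%: 25 × 0.26 = 6.5, 50 × 0.26 = 13, 75 × 0.26 = 19.5, 100 × 0.26 = 26. Firing counts are 7, 14, 20 and 27.

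**First look, true rate at the limit.** P(X ≥ 20 | 25, 0.76) = 0.423. P(X ≥ 7 | 25, 0.26) = 0.485.

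**All four looks.** Exact recursion: hold the distribution of the running count among trials not yet stopped, add a Binomial(25, p) increment, move the mass at or above the boundary to the stopped total, and repeat.

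| Limit | True rate | Chance of a stop by the fourth look |
|---|---|---|
| 76% | 76% | 0.67 |
| 76% | 70% | 0.28 |
| 76% | 60% | 0.03 |
| 76% | 50% | 0.002 |
| 26% | 26% | 0.69 |
| 26% | 20% | 0.28 |
| 26% | 15% | 0.08 |
| 26% | 10% | 0.01 |

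If both arms are pooled (looks at 50, 100, 150 and 200), the figures at the limit are 0.69 (76%) and 0.67 (26%), so the choice of arm hardly changes this calculation.

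**Equal arms.** Suppose 20/25 have any event in each arm. Then 20/25 = 80%, above 76%, and this limb requires a stop. The difference between arms is 0, the chi-square statistic is 0, and Section 10.1 sees no excess. For attributed events, 7/25 in each arm is 28%, above 26%, with the same result.

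**What an allowance for chance costs.** With an exact one-sided 5% bound at 25 men, the firing count becomes 23 for the 76% limit, since P(X ≥ 23 | 25, 0.76) = 0.041. For the 26% limit it becomes 11, since P(X ≥ 11 | 25, 0.26) = 0.039. For a true rate 10 points above the limit:
- True 86%: P(X ≥ 20) = 0.87 as written, P(X ≥ 23) = 0.30 with the bound.
- True 36%: P(X ≥ 7) = 0.85 as written, P(X ≥ 11) = 0.26 with the bound.

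For illustration only, firing counts of 24, 44, 65 and 85 (76% limit) or 12, 20, 28 and 36 (26% limit) hold the four-look chance of a stop at the limit just under 5%.

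**The case against.** Several points on the other side stand.

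- The looks and the safety set do exist, in Sections 10.1 and 6.1. What is missing is a reference to them from the stopping rule, together with correct pointers in Sections 4.2 and 5.1.7.
- An absolute ceiling beside a placebo comparison is a legitimate design. A reader might infer that the two triggers contradict each other. The documents do not show that: the triggers can coexist, and one firing without the other is what separate triggers do. The gap is that the plan never says this is intended.
- The figures of 67% and 69% hold only when the true rate equals the limit. Well below it, the risk is small.
- A reader might infer that any count from 7 to 19 of 25 gives opposite answers under the two columns. That sets one count against two different quantities. If 15 of 25 had any event and 5 of 25 a drug-related one, neither limit would be exceeded (60% against 76%, 20% against 26%). The column is unnamed, but that range does not measure the harm.
- A reader might also apply the urinary retention row (4.5%) to the primary endpoint and conclude that the trial must stop at its own planned rates. This requires reading the table row by row, counting the endpoint as an adverse event and applying no attribution. Section 11.4 lists "their endpoints, secondary measures, adverse events" as separate items, Section 2.3 handles retention as the endpoint, and the toxicity survey does not ask about it.

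The serious-event limb, Section 10.1 and expedited reporting under Section 7.5.1 also remain, so safety oversight does not rest on this limb alone.

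**Conclusion.** The point holds and should be fixed. The first limb is a mandatory rule whose limit, column and arm cannot be read from the text. It has no allowance for chance and no stated relation to Section 10.1. Followed literally, it stops about two trials in three when the true rate equals the listed rate, about 28% when the true rate is six points lower, and 3% or fewer at a true 60% (76% limit) or 10% (26% limit). It can also fire when the arms are equal.

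A reader might go further and infer that a false stop is likely. The documents do not support that, because they do not predict the overall adverse-event rate in this population. The figures are a range over assumed true rates. They rest on four looks of 25 tamsulosin patients, one indicator per patient, and counts matched to their own column.

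**What to change.** Reconcile the Stopping Rules paragraph and Section 10.1 into one stated rule that:

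- names the event category and the matching column, with all-cause counts compared with the all-cause rate and attributed counts with the drug-related rate, and says whether attribution governs this limb;
- names the arm, the safety set (Section 6.1) and the looks (Section 10.1);
- says how the historical rate and the placebo comparison relate, and whether either alone stops the study;
- replaces any numerical excess over a fixed rate with a stated allowance for chance, for example an exact one-sided binomial bound.

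Correct the pointers to Section 5.4 in Sections 4.2 and 5.1.7 so that they lead to the enrolment intervals.

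This is protocol wording only, with no extra patients or procedures. The real cost is sensitivity at early looks. With a one-sided 5% bound at 25 men, the chance of flagging a true 10-point excess falls from 87% to 30% (76% limit) or from 85% to 26% (26% limit), and the sponsor should weigh that when setting the bound. Whether to keep an absolute limit, its level and the serious-event limb remain the sponsor's decisions.

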### 8. DRUG/DEVICE INFORMATION

#### 8.1 Tamsulosin

- Other names for the drug: Flomax™
- Classification: alpha-1 selective alpha blocker
- Mode of action: selective  $\alpha_1$  receptor blocker that has preferential selectivity for the  $\alpha_{1A}$  receptor in the prostate versus the  $\alpha_{1B}$  receptor in the blood vessels
- Storage and stability: stable at room temperature
- Preparation: 0.4 mg capsule
- Route of administration for this study: oral
- Incompatibilities (per Epocrates): amiodarone, dronedarone, boceprevir, chloramphenicol, clarithromycin, cobicistat, conivaptan, cyclosporine, delavirdine, doxazosin, fluvoxamine, fosamprenavir, imatinib, itraconazole, ketoconazole, lopinavir/ritonavir, nefazodone, nelfinavir, posaconazole, prazosin, rifampin/isoniazid, rifampin/isoniazid/pyrazinamide, ritonavir, telaprevir, telithromycin, terazosin, tipranavir, voriconazole
- Availability: commercially available as a generic
- Side effects: Of the more common drug-related side effects, dizziness, abnormal ejaculation, headache, asthenia, postural hypotension, palpitation, dry mouth and impotence per **(10)**. Please refer to the package insert for a comprehensive list of adverse events.
- Nursing implications: no additional duties will be required of Nursing that are not otherwise performed per postoperative protocol for total arthroplasty patients.

**8.2 Return and Retention of Study Drug/Device**

If the patient does not take all of the prescribed capsules, the remaining capsules will be destroyed per University policy.

**9. CORRELATIVES/SPECIAL STUDIES**

No special correlative studies are planned.

**10. STATISTICAL CONSIDERATIONS****10.1 Study Design/Study Endpoints**

Prospective, double blinded, randomized single-center study comparing the efficacy of tamsulosin in reducing POUR incidence in primary total hip and knee arthroplasty patients.

Adverse events will be monitored at intervals of 50 (25 in each group). If AEs in the trial group exceed those in the placebo group, and this difference is statistically significant and related to the active drug (tamsulosin), then the study will be terminated. Minor adverse events will be examined via statistical tests (chi-square) at each interval. If there are severe adverse events noted in the intervention group, the study may be halted until further review.

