**STUDY SCHEMA**

**STUDY SUMMARY**

Title	Prospective, randomized, double-blind, placebo-controlled trial of prophylactic tamsulosin for postoperative urinary retention in primary total hip and knee arthroplasty patients
Short Title	Prophylactic tamsulosin for postoperative urinary retention in hip and knee arthroplasty
Phase	Phase 3
Methodology	Prospective, randomized, double-blind, placebo-controlled
Study Duration	1.5 - 3 years until a prior calculated sample size reached (see above)
Study Center(s)	Single-center
Objectives	Determine if prophylactic tamsulosin given beginning five days prior to surgery through post-op day one reduces the incidence of postoperative urinary retention in total hip and knee arthroplasty patients
Number of Subjects	456 screened with a 50% accrual rate (182 total subjects needed with 20% dropout for a total of 228 patients enrolled)

Control Group	91 patients undergoing primary total hip or knee arthroplasty who are on an $\alpha$ 1-adrenoceptor blocker at the time of surgery
Diagnosis and Main Inclusion Criteria	Postoperative urinary retention in primary total knee and hip arthroplasty patients
Study Product(s), Dose, Route, Regimen	Tamsulosin 0.4 mg p.o. daily
Duration of administration	Five days prior to operation until post-op day one (seven days total)
Reference therapy	Placebo
Statistical Methodology	Two-tailed t-test for primary outcome, (80% power, $\alpha = 0.05$ )

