**10.3 Data Analyses Plans**

Chi-square test will be used to compare the primary outcome of the incidence of POUR between those taking and those not taking tamsulosin at the time of surgery, as well as the secondary measure of the incidence of discharge to a skilled nursing facility between the two groups. T-test will be used to compare the secondary measures of length of hospital stay and postoperative pain medication requirements (average daily dose) between the two groups. Regression analysis will be performed of other postoperative complications including surgical site infection, deep venous thrombosis, pulmonary embolism, urinary tract infection, pneumonia, cardiovascular event, fevers, and the duration of anesthesia between the two groups. Significance will be set at  $\alpha = 0.05$ .

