**Are you experiencing any of the following symptoms?**

1. Dizziness: yes / no
2. Headache: yes / no
3. Palpitations (a rapid, fluttering, or pounding heart): yes / no
4. Fainting: yes / no
5. Drowsiness: yes / no

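### Section 10.1 makes termination mandatory on a significant, drug-related AE excess at repeated looks, with no interim level, no defined AE variable and no severity threshold, so a mild effect the protocol already lists can end the trial

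*Combined protocol and SAP*

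**What the plan says.** Section 10.1 fixes the timing: "Adverse events will be monitored at intervals of 50 (25 in each group"). Three conditions must hold together for the trial to end, namely an excess on tamsulosin, statistical significance, and attribution to the drug: "If AEs in the trial group exceed those in the placebo group, and this difference is statistically significant and related to the active drug (tamsulosin"). The consequence is unconditional: "this difference is statistically significant and related to the active drug (tamsulosin), then the study will be terminated". The following sentence names a test, but for minor events: "Minor adverse events will be examined via statistical tests (chi-square) at each interval". Severe events are handled differently: "If there are severe adverse events noted in the intervention group, the study may be halted until further review".

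Section 10.3 gives the only level in the analysis plan ("Significance will be set at" 0.05), and says nothing about interim looks. Appendix 2 asks "Are you experiencing any of the following symptoms" and lists five yes/no items: dizziness, headache, palpitations, fainting and drowsiness. All five have counterparts in the 7.1.4 table, and section 8.1 names dizziness, headache and palpitation among the more common drug-related effects.

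Two other places bear on the rule. The Stopping Rules after section 7.6 stop the study if the AE rate passes the listed expected rate, or if more than two serious events are judged directly due to the agent. Section 7.4 defines attribution categories for expedited reporting, but does not tie any of them to 10.1.

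**The concern.** A mandatory rule needs a defined variable, test and level. Here the variable could be one overall AE comparison or five separate symptoms, the chi-square could be corrected or not, and the level can only be borrowed from the final analysis. The chance of ending the trial with no true difference depends heavily on these open choices.

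The larger problem is a real effect. Mild dizziness caused by tamsulosin meets all three conditions: it is in excess, it can become significant, and it is drug-related. Nothing in the sentence asks whether the event is serious or already expected. Followed literally, the rule could end the trial at 25 per arm, well short of the 91 per arm that section 10.2 requires for 80% power on urinary retention.

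**Working it through.** **The plan's own figure.** Section 10.2: 40% v 20%, two-sided 0.05, 80% power, continuity correction. Uncorrected n = [1.96√(2×0.3×0.7) + 0.8416√(0.24+0.16)]² / 0.2² = 81.2, that is 82. Corrected n = (81.2/4)[1 + √(1 + 4/(81.2×0.2))]² = 90.9, that is 91. Then 91/0.8 = 113.75, that is 114 per arm and 228 in total. The sample size reproduces. The plan states no error rate for the AE looks, so there is none to reproduce.

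**Number of looks (inferred).** 228/50 = 4.56 gives four looks (25, 50, 75 and 100 per arm). With 182 evaluable, 182/50 = 3.64 gives three.

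**Test.** z = (p_T − p_C) / √[p̄(1−p̄)·2/n], where z² is the uncorrected chi-square. The corrected form subtracts 1/n from the difference. A crossing is z > 1.96 in favour of more AEs on tamsulosin. For one look the nominal chance in that direction is 2.5%.

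**What correction does at the first look.** Take 4/25 v 0/25: p̄ = 0.08, difference 0.16, SE = √(0.08×0.92×2/25) = 0.0767, z = 2.085, chi-square 4.35, p = 0.037. Corrected, the difference is 0.12 and p = 0.118. Fisher's exact p = 0.110. The same data cross or do not cross depending on a detail the plan leaves out.

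**No true difference.** Simulation of 100,000 trials, cumulative looks. Symptoms are taken as independent, and every flag is counted as drug-related.

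| AE variable | Looks | Uncorrected | Corrected |
|---|---|---|---|
| One overall, assumed 30% rate | 3 | 5.4% | 3.1% |
| One overall, assumed 30% rate | 4 | 6.5% | 4.0% |
| Five symptoms, 7.1.4 rates (8.5, 4.7, 2.7, 1.0, 0.8%) | 4 | 15% | 4% |
| Five symptoms, each assumed 10% | 4 | 28% | 12% |
| Five symptoms, each assumed 20% | 4 | 29% | 17% |
| Five symptoms, each assumed 30% | 4 | 28% | 18% |

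Over assumed rates of 5–30%, one overall variable at four looks gives about 5–7% uncorrected and 1.5–4% corrected.

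**Effect of the relatedness condition.** For five symptoms at 20%, if a flagged symptom is judged related with probability 1, 0.5, 0.25 or 0, the uncorrected figure is 29%, 16%, 8% or 0%.

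**A real listed effect.** Section 7.1.4 gives drug-related dizziness as 5.8%. Assume that this is the true excess over placebo. With four looks at dizziness alone, the uncorrected test crosses in about 42%, 32% and 25% of trials at an assumed background of 5%, 10% and 20%. The corrected test crosses in about 27% at the lowest background and 18% at the highest. With three looks the uncorrected range is about a fifth to a third.

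**The case against.** The strongest reply is that 10.1 does not end the trial on significance alone. The excess must also be related to tamsulosin, and a chance excess stops nothing unless someone attributes it to the drug. That stands, and it makes every no-difference figure an upper value. A reader might infer that any nominally significant excess stops the trial; the sentence does not say so.

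Per-symptom testing is also an inference. Section 4.2 speaks of comparing overall cohort safety, which favours a single comparison, and then the inflation is modest. With continuity correction it largely disappears. Chi-square itself is named for minor events, not in the termination sentence, although it is the only interim test named. All of this stands.

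A reader might further infer that the severity order is inverted, with minor events ending the trial while severe ones only may halt it. The documents do not support that. The severe-event sentence needs no test, comparison or attribution, so it has a lower threshold with discretion, and the Stopping Rules mandate a stop for more than two serious events due to the agent.

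Finally, the 25–42% is not a false-alarm rate: it is the rule detecting a real effect. The 5.8% is also a drug-related frequency from a reference on long-term treatment, not a placebo-subtracted excess after seven capsules. Both points are correct. Tolerating extra alarms for harm in a prophylaxis trial is a legitimate choice, but the plan should make it openly, and it does not explain why a mild expected effect should end the trial without review.

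**Conclusion.** The concern holds in a limited form. The rule is mandatory, repeated, and silent on level, variable and severity. The most secure part needs no argument from chance: a real, mild, listed effect satisfies every condition. How often that would happen rests on the assumed 5.8-point excess and 5–20% background.

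The chance component is small for one overall variable and becomes large only if five symptoms are tested separately without correction. Those figures rest on an inferred number of looks, the 0.05 level carried over from 10.3, assumed symptom rates where stated, and independence between symptoms. The sample size in 10.2 is not in question; an early stop would simply forgo the power it provides.

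**What to change.** In section 10.1:

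- Name one overall AE comparison for the interim by-arm test, and report individual symptoms descriptively.
- State the exact test, including whether it is continuity-corrected, and its interim level. Give the false-flag rate and the power to detect harm for that same test.
- Make a significant excess of minor events lead to a safety review instead of automatic termination.
- Reconcile this limb with the severe-event sentence in 10.1 and with the Stopping Rules after section 7.6, so that it is clear which governs when they differ.

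The change is wording only, but a stricter level has a safety cost. As an illustration with four looks, a Pocock-type critical value of 2.361 (nominal two-sided p of 0.0182) on one uncorrected comparison brings the false-flag rate to 2.5% at an assumed 30% rate. For a true 15-point excess on an assumed 20% background, the chance of a formal flag falls from about 73% at the 0.05 level to about 57% with that chi-square, and to about 50% with Fisher's exact test at the same nominal level, where false flags are only about 0.5–1.5%. The level should be chosen with these figures in view.
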